# **HRP-503** Protocol Template

Instructions:

- 1. Prepare a document with the following sections. Note that, depending on the nature of your research, certain sections below may not be applicable. Indicate N/A as appropriate, explaining where possible.
- 2. For any items described in the sponsor's protocol, grant application or other source documents submitted with the application, you may reference the title and page numbers of these documents rather than cutting and pasting into this document. Do NOT refer to any derived documents, such as the Sample Consent document, or other internal documents required with the submission.
- 3. If you reference page numbers, attach those pages to this protocol.
- 4. When you write a protocol, keep an electronic copy. You will need to modify this copy when making changes.

### Brief Summary of Research (250-400 words):

The purpose of this study is to see if the Negative Pressure Wound Therapy (NPWT) system is effective and safe for the prevention of superficial and deep incisional surgical site infections (SSI) in high risk patients within 30 days after elective colorectal surgery. It has been shown that patients with an IBD, patients undergoing a reoperation or patients with certain comorbidities are at a higher risk of developing an SSI. The NPWT device is a wound dressing with a vacuum system that can be placed over abdominal wounds. The study will include up to 400 patients at this single site, where these high risk patients will be randomized to receive either one of two arms. The first arm involves the placement of the NPWT device in the immediate postoperative period over abdominal wounds after clean-contaminated and contaminated colorectal surgical procedures. The device would then be left on for 5 days. The second arm would be standard of care and would entail routine postoperative protocols. Subjects will then be seen once at a 30 day ( $\pm$  7 days) follow-up visit to assess for the development of SSIs.

### 1) Objectives:

Research Question: Does the application of the NPWT device immediately after surgery work and is it safe for the prevention of superficial and deep incisional surgical site infections (SSI) in high risk patients within 30 days after elective colorectal surgery when compared to standard of care of the same population?

### 2) Background

Surgical site infections (SSIs) are a common cause of nosocomial infections, and a major contributor to patient morbidity, mortality and unnecessary healthcare costs

	Protocol Title:	Prophylactic Negative Pressure Wound Therapy to Reduce Surgical Site Infections in Elective Clean-Contaminated Colon Resections
	Principal Investigator Name/Contact Info:	[name] [name], [contact]
Mount	Primary Contact	[name]
Sinai	Name/Contact Info	[name], [contact]
	Date Revised:	10/10/2018
	Study Number:	

(1,2). The overall SSI rate in elective, clean-contaminated colon resections has been reported as high as 25%, the highest SSI rate among all elective surgical procedures (1). There has been a national trend in instituting pre-operative and post-operative measures to prevent SSIs (colon bundle), which was found to reduce the relative SSI rate by over 50% (3). At the Mount Sinai Hospital, the colon bundle protocol includes bowel decontamination by mechanical preparation and/or oral antibiotics, monitoring and maintenance of a normal perioperative glycemic index, hair clipping outside the OR, a preoperative chlorhexidine wash, a wound protector, intravenous antibiotics, a separate closing tray, and changing of sterile scrubs prior to closing. The colon bundle was first instituted in 2014 at Mount Sinai, and despite these efforts, while the overall SSI rate has declined, for high-risk, clean-contaminated cases in patients with inflammatory bowel diseases (IBD) or who are undergoing re-operative bowel surgery, the SSI rate remains at around 25%.

Negative pressure incision wound therapy represents a possible opportunity to reduce SSIs in colorectal surgery even further. This technology was initially studied in orthopedics and later in trauma surgery. In colorectal surgery, a retrospective study assessed the use of negative pressure incision wound therapy applied in clean-contaminated cases, compared to standard of care, and found a greater than 50% reduction in the SSI rate (4). However, the intraoperative use of NPWT applied immediately following skin closure has not yet been determined in a prospective, randomized fashion to reduce SSI in clean-contaminated colon resection cases (5).

## 3) Setting of the Human Research

Informed consent will be obtained in the offices of one of the investigators while the patient is in for an office visit or at the Mount Sinai Pre-Surgical Testing Center before the patient's screening visit. No study related tests will be performed prior to informed consent. The screening visit and surgery will take place at Mount Sinai Medical Center. The follow-up visits will take place at either the Mount Sinai Medical Center or at Mount Sinai-affiliated off-site practices. Statistical analyses will be performed on de-identified data at Mount Sinai in collaboration with the Department of Biostatistics.

### 4) Resources Available to Conduct the Human Research

There are multiple investigators involved in this study in addition to the Principal Investigator, [name] M.D. The Principal Investigator and Co-Investigators all have extensive experience conducting research at the Mount Sinai Medical Center. Additionally, a research coordinator is employed and will be involved in the consent and data collection processes. Prior to participation, each of the investigators will have read the protocol and understand what it involves and what each of their specific responsibilities entail. The recruitment goal for this study is about 400 patients in 24 months. The investigators conduct about 83 clean/contaminated bowel resections each month. In order to meet the recruitment goal, between 15 and 20 patients would need to be consented each month. Because the vast majority of the study data-points are derived from the standard of care perioperative assessments, intraoperative clinical documentation, and the standard of care follow-up visits, meeting this screening and enrollment goal is feasible.

## 5) Study Design

## a) Recruitment Methods

The research coordinator and the investigators will screen the office schedules of the investigators for patients presenting for clean/contaminated colorectal surgeries. A HIPAA waiver was submitted to the IRB to allow the study coordinator to access names, telephone numbers, and medical record numbers (MRN) to inform an investigator of the patient's potential eligibility. Other PHI identifiers have the potential to be seen since the pre-screening does involve opening the electronic medical records of these patients. However, the study team is only specifically looking for elements of PHI that would help them to determine eligibility and be able to identify the patient for consenting (name, MRN, date of birth, date of surgery). After identifying the possible patient, the investigator will approach the patient about the study, to see if the patient is interested. If the patient's office visit or prior

	Protocol Title:	Prophylactic Negative Pressure Wound Therapy to Reduce Surgical Site Infections in Elective Clean-Contaminated Colon Resections
	Principal Investigator Name/Contact Info:	[name] [name], [contact]
Mount Sinai	Primary Contact Name/Contact Info	[name] [name], [contact]
	Date Revised:	10/10/2018
	Study Number:	

to a scheduled screening visit. The patient will not be considered enrolled until it is determined that they have met all inclusion criteria and do not meet any exclusion criteria the day of the procedure.

## b) Inclusion and Exclusion Criteria

All patients from aged 18 or older who will undergo an open or laparoscopicassisted clean-contaminated or contaminated colorectal surgical procedure will be included if they meet the following criteria. Patients must either have an inflammatory bowel disease, undergoing a stoma reversal, undergoing reoperation within 30 days, or have two or more of the following risk factors: presence of an ostomy, creation of an ostomy, type II diabetes, BMI greater than 30, immunosuppression, malnutrition, current smoker, chronic kidney disease (creatinine > 1.2), and disseminated cancer. Exclusions include patients currently enrolled in another interventional clinical trial, patients with a current infection (including a known urinary tract infection), patients allergic to or hypersensitive to silver, patients planning to undergo a second colorectal surgical procedure (e.g., colostomy or ileostomy takedown) or any other general surgery in less than 30 days of index-surgery, any patient in which the planned surgery would include: i) placement of a stoma in the principal incision; ii) placement of a drain into the supra-peritoneal fascia space that emerges through the principal incision; iv) placement of a drain into the intraperitoneal space that emerges through the principal incision; and v) supplementation of any of the irrigation fluid with antibiotic or antiseptic drugs, patients with healing disorders, pregnant women, prisoners, or any patient that is deemed unsuitable for the study by the Principal Investigator or the operating surgeon/Co-Investigator.

## c) Number of Subjects

Up to 400 subjects are expected to be consented at this site. A series of 330 high risk patients undergoing elective, open or laparoscopic-assisted, clean contaminated cases involving colon resection will be enrolled in this study, of which 110 patients will receive an intraoperative application of NPWT and 220 control patients will receive the standard of care. This number was chosen based on a power analysis. Assuming the NPWT group will have a 50% reduction from the current clean-contaminated colon resection SSI rate of approximately 25%, a two-sided, chi-square power analysis indicated that with a 2:1, control to experimental ratio, 330 total subjects will be needed to detect this difference with 80% power. This number was rounded up to a

	Protocol Title:	Prophylactic Negative Pressure Wound Therapy to Reduce Surgical Site Infections in Elective Clean-Contaminated Colon Resections
	Principal Investigator	[name]
	Name/Contact Info:	[name], [contact]
Mount	Primary Contact	[name]
Sinai	Name/Contact Info	[name], [contact]
	Date Revised:	10/10/2018
	Study Number:	

total of 400 patients expected to be consented in order to account for screen failures, changes in operative and post-operative treatments, and subjects lost to follow-up. These patients will be allocated to each study arm using a simple randomization scheme. Mount Sinai performed almost 1,000 clean-contaminated colon resections in 2015, and we believe the proposed study can be completed in less than 2 years from the first enrollment.

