### 10) Economic Impact on Subjects

The cost of the NPWT device will be paid for by KCI Inc. The expense of any tests, or treatments related to standard medical care will be billed to the subject or the subject's insurer in the regular way.

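### Section 5c: 330 patients split 2:1 towards control give about 77% power at a two-sided 5% level, not the stated 80%, and no reason is given for the ratio; 1:1 at the same total gives about 83%

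*Combined protocol and SAP*

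**What the plan says.** Section 5c (Number of Subjects) fixes the arms: 330 patients, "of which 110 patients will receive an intraoperative application of NPWT and 220 control patients will receive the standard of care". The basis is given in the same paragraph. The assumed effect is "Assuming the NPWT group will have a 50% reduction", starting at a current rate of about 25%. The test is a two-sided chi-square, and the conclusion drawn is: "with a 2:1, control to experimental ratio, 330 total subjects will be needed to detect this difference with 80% power". Alpha is not stated there or elsewhere. Allocation is by simple randomisation.

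Section 5d (Study Timelines) carries the same ratio into the interim analysis, with 55 treated and 110 control patients.

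No section explains why the ratio is 2:1 or why control is the larger arm. Two related facts appear but are not offered as reasons. Section 4 describes recruitment as feasible, and section 10 says "The cost of the NPWT device will be paid for by KCI Inc".

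Section 1 (Objectives) asks about both efficacy and safety: does the device "work and is it safe for the prevention of superficial and deep incisional surgical site infections". Section 5e lists serious adverse events as a secondary outcome.

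**The concern.** At a fixed total, for rates near 25% and 12.5%, a 2:1 split towards control gives less power than 1:1. Unequal allocation is usually chosen for a stated purpose, such as limited device supply, cost, or more experience with the new treatment. Here the smaller arm is the new treatment, and no purpose is stated.

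Two things are at stake. The first is whether the stated 80% power is what the stated design delivers. The second is whether power and device experience are being given up for nothing the plan identifies. Only patients who receive the device can inform on device reactions, such as those listed in section 6.

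**Working it through.** **Inputs.** Control rate p1 = 0.25, device rate p2 = 0.125 (half of 25%), difference d = 0.125, two-sided chi-square test, target power 80%, arms 220 and 110 (all section 5c). Alpha = 0.05 is an assumption.

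**Formula (pooled chi-square).** With arm sizes n1 (control) and n2 (device), and p̄ = (n1·p1 + n2·p2)/(n1 + n2):
- SE0 = √[p̄(1 − p̄)(1/n1 + 1/n2)]
- SE1 = √[p1(1 − p1)/n1 + p2(1 − p2)/n2]
- Power = Φ[(d − 1.96·SE0)/SE1]

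**Step 1: the plan's design, 220 control and 110 device.** p̄ = 68.75/330 = 0.2083, SE0 = 0.0474, SE1 = 0.0430. Power = Φ(0.746) = **77.2%**. Exact enumeration of the Pearson chi-square test gives 77.7%. The same formula needs 235 + 118 = 353 patients for 80% at this ratio, which is 23 more than stated.

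**Step 2: can 330 be reproduced?** For total N at 80% power:

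| Method | N |
|---|---|
| Pooled, 2:1 towards control (as written) | 353 |
| Pooled with continuity correction, 2:1 towards control | 389 |
| Pooled, 2:1 towards device (110 control, 220 device) | 330 |
| Arcsine, 2:1 | 336 |
| Pooled with unweighted mean rate, 2:1 towards control | 333 |
| Unpooled, 2:1 towards control | 306 |
| Pooled, one-sided, 2:1 towards control | 276 |

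With the arms reversed, p̄ = 55/330 = 0.1667, SE0 = 0.0435, SE1 = 0.0469, and power = Φ(0.846) = 80.1%. That is an exact match to 330. The arcsine and unweighted-mean variants come close without reversal.

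**Step 3: 1:1 at the same total, 165 and 165.** p̄ = 0.1875, SE0 = 0.0430, SE1 = 0.0424. Power = Φ(0.961) = **83.2%** (exact 83.7%). At 1:1, 80% power needs 304 patients.

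**Step 4: sensitivity, total 330.**

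| Setting | 220/110 | 165/165 |
|---|---|---|
| Alpha 0.10 | 86.3% | 90.0% |
| Alpha 0.05 | 77.2% | 83.2% |
| Alpha 0.025 | 66.8% | 75.1% |
| Alpha 0.01 | 52.6% | 63.2% |
| Continuity correction, approximate | 72.1% | 79.3% |
| Continuity correction, exact (Yates) | 73.0% | 80.3% |
| Arcsine | 79.3% | 83.8% |
| Unpooled | 82.9% | 83.8% |
| Control rate 20%, halved | 64.6% | 72.2% |

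Rows below the alpha rows use alpha 0.05. 1:1 is better in every row, by 1 to about 11 points.

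**Step 5: device safety.** If no event is seen, the one-sided 95% upper bound on its rate is 1 − 0.05^(1/n): 2.7% for n = 110 and 1.8% for n = 165. The chance of at least one case of a 1% reaction is 1 − 0.99^n: 67% and 81%. For a 0.5% reaction it is 42% and 56%.

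**The case against.** Unequal allocation is valid and unbiased, so a missing rationale may need only a sentence. The power shortfall can also be cured without touching the ratio: 353 patients at 2:1 give 80.2%, and section 5d already lets the interim adjust enrolment. Both points stand, which is why keeping 2:1 with a stated reason and a corrected power figure is an acceptable answer.

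The size of the loss depends on the formula: 6.0 points pooled, 4.5 arcsine, 1.0 unpooled. This stands as a caution. However, the plan names a chi-square test, and exact enumeration of that test gives 77.7% at 220/110, so the shortfall does not come from the pooled approximation.

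Several stronger readings are tempting, and the documents do not support them:
- *The ratio was certainly entered the wrong way round.* The exact match at 330 suggests it, but two other methods land within six patients without reversal. It is a reason to check, not a finding.
- *1:1 guarantees 80%.* It does so at alpha 0.05 without a continuity correction and with a control rate near 25%. At alpha 0.025, or with a control rate of 20%, it does not.
- *The control rate is already well known.* The site's figure of about 25% in section 2 covers IBD or re-operative clean-contaminated cases. Section 5b enrols a wider group.
- *110 is too few for safety and 165 is enough.* The plan sets no safety precision target, and neither number is informative on rare reactions.
- *The change is free.* Section 10 says who pays for the device, but not how many devices are covered. The 2:1 ratio does save 55 of them.

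**Conclusion.** The point holds in a limited form. At an assumed two-sided alpha of 0.05 and rates of 25% and 12.5%, the design in section 5c has about 77% power, roughly 3 points below the figure stated. The documents give no reason for favouring control. The same 330 patients at 1:1 would have about 83% power, or 79% to 80% if a continuity correction is used. The advantage of 1:1 does not depend on the alpha assumed; reaching 80% does. The safety gain from 55 more device patients is real but modest. The 2:1 ratio is not an error in itself. What needs correcting is an unexplained ratio combined with a power statement that the stated arms do not deliver. Simple randomisation will make the achieved arm sizes vary around their targets under either ratio.

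**What to change.** In section 5c, state alpha, show the power calculation, and confirm which arm was the larger in it. Then do one of the following:

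1. Allocate 1:1 (165 NPWT, 165 control) at the same total of 330, restate power as about 83%, and change the interim split in section 5d to about 82 per arm.
2. If device supply or another reason requires 2:1 towards control, state that reason and restate power as about 77% (or raise the total to about 353 to keep 80%).

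Option 1 costs a protocol and randomisation-list amendment and about 55 more devices (165 − 110), whose supply the manufacturer would need to confirm. The patient total does not change.

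If patients have already been randomised 2:1, apply 1:1 from the amendment onwards and stratify the primary test by allocation period. The gain is then smaller. With half of the 330 already enrolled at 2:1, the expected arms are 110 + 82.5 = 192.5 control and 55 + 82.5 = 137.5 device, and power is about 81.6% before stratification.

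### The stated 80% power does not follow from the plan's own inputs: 220 controls and 110 NPWT patients give about 77%, and 80% at that split needs about 350 patients

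*Combined protocol and SAP*

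**What the plan says.** All the planning figures are in protocol section 5c (Number of Subjects).

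- **Test:** "a two-sided, chi-square power analysis indicated" the required number. No significance level is given there or elsewhere.
- **Rates:** the control rate is the "current clean-contaminated colon resection SSI rate of approximately 25" per cent, and the effect is set by "Assuming the NPWT group will have a 50% reduction", which makes the NPWT rate 12.5%.
- **Allocation:** "with a 2:1, control to experimental ratio", so that "110 patients will receive an intraoperative application of NPWT and 220 control patients will receive the standard of care".
- **Result:** "330 total subjects will be needed to detect this difference with 80% power".
- **Attrition:** 330 is raised to a "total of 400 patients expected to be consented in order to account for screen failures", changes in treatment and loss to follow-up.

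Section 5d repeats the direction of the split: the interim analysis is set at 55 treated and 110 control patients.

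**The concern.** The section names the test, its sidedness, both rates, the ratio and the arm sizes, so only alpha is missing and the power can be recomputed directly. At the conventional alpha it comes out below the stated figure.

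This is the plan's only justification for its sample size. If 80% is not a property of the 220/110 design, the plan understates the chance of a false-negative result at the effect it was built to detect. Anyone who rechecks the paragraph will find the mismatch.

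**Working it through.** **Inputs (section 5c):** control rate p_c = 0.25; NPWT rate p_t = 0.125; difference 0.125; n_c = 220; n_t = 110; two-sided chi-square test. **Assumption:** alpha = 0.05, so z = 1.96.

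**1. Power of the stated design, pooled-variance formula**

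- Pooled rate: (220 × 0.25 + 110 × 0.125) / 330 = 0.2083
- Standard error under no difference: SE0 = √[0.2083 × 0.7917 × (1/220 + 1/110)] = 0.0474
- Standard error under the planned difference: SE1 = √[0.25 × 0.75/220 + 0.125 × 0.875/110] = 0.0430
- Power = Φ[(0.125 − 1.96 × 0.0474) / 0.0430] = **77.2%**

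The stated 80% is not reproduced.

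**2. The same design without an approximation to power**

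Summing the binomial probabilities of every outcome pair that the test would reject gives **77.7%** for the Pearson chi-square and 73.0% with the Yates correction.

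**3. Patients needed for 80% at 2:1**

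Per NPWT arm: n_t = [1.96 × √(1.5 × 0.2083 × 0.7917) + 0.8416 × √(0.125 × 0.875 + 0.25 × 0.75/2)]² / 0.125² = (0.9749 + 0.3793)² / 0.015625 = 117.4

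That rounds up to 118 NPWT patients. With 235 or 236 controls the total is 353 or 354. By enumeration of the Pearson test, 230/115 (345) gives 79.9% and 232/116 (**348**) gives 80.3%. Against 330, the shortfall is 18 to 24 patients: 18/330 = 5% and 24/330 = 7%.

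**4. Could another method have produced 330?**

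| Calculation, 25% vs 12.5%, two-sided 0.05 unless noted | Power at 220/110 | Total N for 80% at 2:1 |
|---|---|---|
| Pooled-variance chi-square formula | 77.2% | 353–354 |
| Exact enumeration, Pearson | 77.7% | 348 |
| Noncentral chi-square | 75.0% | 375 |
| Log odds ratio | 73.4% | about 387 |
| Arcsine | 79.3% | 336 |
| Unpooled variance | 82.9% | 309 |
| One-sided 0.05, pooled formula | 86.3% | 276 |

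None of these gives 330. A pooled rate that ignores the 2:1 weights comes close, at 333.

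**5. Effect of the split**

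| Control / NPWT | Formula power | Exact Pearson power |
|---|---|---|
| 220 / 110 (planned) | 77.2% | 77.7% |
| 165 / 165 | 83.2% | 83.7% |
| 110 / 220 (reverse of the plan) | 80.1% | 80.8% |

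With the ratio turned round, the pooled formula needs 110 controls and 220 NPWT patients, exactly 330 in total. A ratio entered the wrong way round would therefore explain the figure, but the documents cannot show that this happened.

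**6. How far the inputs would have to move**

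At 220/110, formula power reaches 80% only if one of these changes:

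- alpha is about 0.06;
- the NPWT rate is about 12.1% rather than 12.5%, with the control rate at 25%;
- the control rate is about 26.3%, with the halving kept.

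**The case against.** The strongest reply is that the gap is small and rests on soft inputs. It is 2.3 to 2.8 points of power. The control rate is given only as approximate: keeping the 50% reduction, 24% gives 74.9% and 26% gives 79.4%, so an error of about 1.3 points in that rate matters as much as the whole discrepancy. Alpha is unstated, no software or formula is named, and common approximations fall on both sides of 80%. The consent ceiling of 400 and the interim analysis in section 5d, which lets enrolment be adjusted, both leave room for a larger trial.

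Part of this stands. The shortfall is modest and does not invalidate the design, and alpha 0.05 is an assumption. The rest does not rescue the figure:

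- An alpha of 0.06 is not a usual level, and a smaller alpha widens the gap (66.8% at 0.025).
- The arcsine and unpooled results come from calculations other than the named chi-square test, whose exact power stays below 78%.
- Uncertainty about the 25% cuts both ways, and 25% is the value the plan itself used.
- The 400 is already assigned to screen failures, treatment changes and losses.
- Section 5d gives no rule for changing enrolment, and checking event rates would not expose an error in the calculation.

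It would also be wrong to blame 2:1 allocation as such, since the reverse split reaches 80.1%. What costs power is putting the smaller arm on NPWT.

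**Conclusion.** The concern holds. With the stated test, rates, ratio and arm sizes, and a two-sided alpha of 0.05, the planned trial has about 77% power (77.2% by formula, 77.7% exact), not 80%. The chance of missing a true halving from 25% is 22 to 23%. At 2:1 in favour of control, 80% needs 348 to 354 patients. With the Yates correction the shortfall would be larger. The conclusion depends on the assumed alpha, but no conventional two-sided level from 0.05 down restores the claim. The origin of 330 cannot be settled from the documents.

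**What to change.** **Needed:** in section 5c, replace the power statement with one that matches the design. For example: with 220 control and 110 NPWT patients, SSI rates of 25% and 12.5%, and a Pearson chi-square test at two-sided alpha 0.05, power is about 77%. If another alpha is intended, state it and recompute. The sponsor should also check which way round the ratio was entered in the source calculation. The cost is one sentence and a slightly less favourable figure, with no change to design or enrolment.

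**Optional, only if the 80% claim is to be kept:**

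- Keep 2:1 and enrol about 350. This fits under 400 consented, but the margin for losses falls from 70/400 = 17.5% to 50/400 = 12.5%.
- Keep 330 and randomise 1:1 (165/165), for about 83%. This is a design trade-off, not a correction. It needs 165 − 110 = 55 more devices and new interim counts in section 5d. Section 10 says the manufacturer pays for the device, but not how many it has agreed to fund.

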## f) Procedures Involved in the Human Research

Subjects will be consented prior to each eligible surgery. Prior to surgery, each prospective subject will be interviewed by a member of the study team and a medical history will be obtained. Randomization will occur prior to the start of surgery. The subject will then undergo their scheduled surgery and if they are placed in the experimental arm, they will receive the negative pressure wound therapy. If the subject is in the control arm, they will receive the standard of care wound dressings. Post-operatively, each patient will be followed for up to 37 days and monitored for the development of an SSI and secondary outcomes. If there is no evidence of a wound infection by post-operative day 5, the NPWT device will be removed. A follow-up, outpatient assessment at 30 days ( $\pm$  7 days) post-operatively will be included for all patients who did not develop a SSI.

It is anticipated that approximately 2% or less of subjects enrolled into this study will require re-operation of the principal incision for within 5-7 days after the original surgery due to various life-threatening complications which may include bleeding, anastomotic dehiscence or other septic complications. For subjects requiring re-

	Protocol Title:	Prophylactic Negative Pressure Wound Therapy to Reduce Surgical Site Infections in Elective Clean-Contaminated Colon Resections
	Principal Investigator	[name]
	Name/Contact Info:	[name], [contact]
Mount	Primary Contact	[name]
Sinai	Name/Contact Info	[name], [contact]
	Date Revised:	10/10/2018
	Study Number:	

intervention, who did not develop an SSI prior to the reoperation, the NPWT device will be re-applied and the study period re-defined based on the latter procedure.

	Screening ≤ 30 days preop	Baseline	Day 1	Day 2	Day 3	Day 4	Day 5	Final Visit 23 to 37 days post op
Study Activity								
Informed Consent	X							
Enrollment Criteria	Х							
Demographic/ Clincal Information		X						
Medical History	Х							
Inclusion/Exclusion Criteria	Х							
Randomization		Х						
Surgery		Х						
Application of NPWT Device		Х						
Bloodwork	Х			X*			X*	
SSI Assessment		Х	Х	Х	Х	X	Х	Х
AE Monitoring	Х	Х	Х	Х	Х	Х	Х	Х
Concomitant Medications	Х	Х	Х	Х	Х	Х	Х	Х

Study schedule of events. \* indicates that study event may occur with 24 hours of study visit.

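### Section 5c uses 330 as the number needed, the number enrolled and (with 5d) the number completing, so on that wording nothing is held in reserve for losses after randomisation, while other sections imply up to 400 randomised

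*Combined protocol and SAP*

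**What the plan says.** The sample size is set in Section 5c, Number of Subjects. On consent: "Up to 400 subjects are expected to be consented at this site". On enrolment: "A series of 330 high risk patients undergoing elective, open or laparoscopic-assisted, clean contaminated cases involving colon resection will be enrolled in this study". The arms are given as: "110 patients will receive an intraoperative application of NPWT and 220 control patients will receive the standard of care". The basis is: "Assuming the NPWT group will have a 50% reduction from the current clean-contaminated colon resection SSI rate of approximately 25" percent; "a two-sided, chi-square power analysis indicated that with a 2:1, control to experimental ratio", 330 in total gives 80% power. The section then raises 330 to 400 expected to be consented, "in order to account for screen failures, changes in operative and post-operative treatments, and subjects lost to follow-up". The next sentence says that these patients will be allocated by simple randomisation.

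Two other sections fix the timing. Section 5a: "The patient will not be considered enrolled until it is determined that they have met all inclusion criteria", which it ties to the day of the procedure. Section 5f: "Randomization will occur prior to the start of surgery".

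Three further places bear on which number is the target:

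- The Brief Summary has the study including up to 400 patients, who are randomised.
- Section 4 gives a recruitment goal of about 400 in 24 months.
- Section 5d sets the interim analysis at about half of the subjects having completed 30-day follow-up, given as 55 treatment and 110 control, and lets planned enrolment be adjusted afterwards.

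The protocol states no alpha, no screen-failure rate, no loss-to-follow-up rate and no analysis set.

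**The concern.** An allowance for attrition works only if it sits before the stage at which the attrition happens. Here the margin lies between consent and enrolment. Screen failures belong there. Loss to follow-up and post-operative treatment changes do not, because they arise in patients who are already enrolled and randomised. If randomisation stops at 330, extra consents replace none of them, and the analysed number falls below the number on which power was computed.

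Two things are at stake. One is a stated power that the trial would not have. The other is a gap in the analysis plan: treatment changes are listed among the reasons for the margin and no analysis set is defined, so it is left open whether a randomised patient whose treatment changed still counts. Changes during or after surgery may be related to SSI risk, so leaving such patients out could bias the comparison.

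**Working it through.** **Inputs.** From 5c: control SSI rate p1 = 0.25; NPWT rate p2 = 0.125 (half of 0.25); n1 = 220 control, n2 = 110 NPWT; two-sided chi-square. Assumed: alpha 0.05, z = 1.960. Loss rates of 5% and 10% are also assumed.

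**1. The plan's own figure.** The pooled-variance formula for the chi-square test is

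power = Φ{ [ (p1 − p2) − 1.960·s0 ] / s1 },

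with s0 = √[ p̄(1 − p̄)(1/n1 + 1/n2) ] and s1 = √[ p1(1 − p1)/n1 + p2(1 − p2)/n2 ].

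- p̄ = (220 × 0.25 + 110 × 0.125)/330 = 0.2083
- s0 = √[ 0.2083 × 0.7917 × (1/220 + 1/110) ] = 0.04742
- s1 = √[ 0.1875/220 + 0.109375/110 ] = 0.04297
- power = Φ[ (0.125 − 1.960 × 0.04742)/0.04297 ] = Φ(0.746) = 77.2%

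Exact enumeration of the Pearson test gives 77.7%. The stated 80% at 330 is therefore not reproduced under the named test; the pooled formula needs 353 to 354. Other formulas come closer or pass: arcsine gives 79.3% at 330, and the unpooled formula 82.9%. This gap exists with no loss at all and is separate from where the allowance sits.

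**2. The roles of 330.**

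| Role | Where | Number |
|---|---|---|
| Needed for 80% power | 5c | 330 |
| Enrolled | 5c | 110 + 220 = 330 |
| Completing follow-up | 5d: 55 + 110 = 165 is about half | about 2 × 165 = 330 |

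The three agree only if nobody is lost after enrolment. The margin is 400 − 330 = 70, or 70/400 = 17.5% of consents, for all causes together.

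**3. When each listed cause occurs.** Screen failures come before enrolment. Operative changes can fall on either side: the schedule in 5f allows screening up to 30 days before surgery, and several exclusions in 5b concern the planned operation, so a changed plan can surface before enrolment, while a change made during surgery comes after it. Post-operative changes and loss to follow-up must come after enrolment and randomisation.

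**4. Power if randomisation stops at 330.**

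| Assumed loss | Analysed (control/NPWT) | Exact | Pooled formula |
|---|---|---|---|
| 0% | 330 (220/110) | 77.7% | 77.2% |
| 5% | 313 (209/104) | 75.5% | 74.8% |
| 10% | 297 (198/99) | 73.3% | 72.5% |

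Loss itself costs 77.7 − 75.5 = 2.2 points at 5% and 77.7 − 73.3 = 4.4 points at 10%.

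**5. Number to randomise so that 330 are analysed,** N = 330/(1 − d), rounded up: 330/0.95 gives 348; 330/0.90 gives 367; 330/0.825 = 400.

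**6. Power if 400 are randomised 2:1.** With no loss (267/133), exact power is 85.7%. With 10% loss, 360 remain (240/120) and it is 81.3%. This is a ceiling: every screen failure among 400 consents lowers the number randomised, and 70 of them bring it back to 330.

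**The case against.** The strongest reply is that no sentence says randomisation stops at 330. The Brief Summary, the goal in Section 4 and the allocation sentence that directly follows the 400 in 5c all support up to 400 entering, with 330 as the evaluable number. The completer counts in 5d fit that reading, and 5d also allows enrolment to be adjusted after the interim. The margin would then cover later losses at least in part. This stands, and it is why a reader should not infer that the design cannot deliver 330 analysed. It does not remove the problem, because 5c also says that 330 will be enrolled as 110 and 220, and both statements cannot be the target.

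A second reply is that most of the distance from 80% should not be charged to attrition. This stands in part: 80 − 77.7 = 2.3 points are missing before any loss, and the remainder depends on assumed loss rates. Under the unpooled formula, 330 would hold 80% up to about 6% to 7% loss (1 − 308/330 = 6.7%), although pooling the variance is what matches the named chi-square test.

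A third concerns exclusions. A reader might infer from the listed reasons that randomised patients with changed treatment will be dropped and replaced. No passage says so, and enlarging a sample for non-adherence and loss is compatible with analysing everyone as randomised. What remains is silence about the analysis set.

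**Conclusion.** The concern holds as an unreconciled enrolment target. On the wording of 5a, 5c, 5d and 5f, 330 is at once required, enrolled and completing, with nothing held back for losses after randomisation. On the wording of the Brief Summary, Section 4 and the allocation sentence in 5c, up to 400 may be randomised. The power the trial can claim depends on which applies: about 73% to 76% at 10% to 5% loss if 330 are randomised, or about 81% at 10% loss if 400 are.

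These figures rest on two-sided alpha 0.05, the plan's rates of 25% and 12.5%, a 2:1 split and assumed loss rates; the protocol gives neither alpha nor a loss rate. The documents do not support the stronger conclusions that 330 analysed is unattainable or that biased replacement is planned. This should be corrected, with medium confidence about the size of the effect.

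**What to change.** In Section 5c, state three numbers separately: consented, randomised and expected to be analysed. Give one assumed rate for screen failure and another for loss after randomisation, and state alpha and the power formula. Bring the Brief Summary, Section 4 and Section 5d into line.

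- If 330 is the number randomised, restate power as about 78% with full follow-up and 73% to 76% at 10% to 5% loss.
- If up to 400 are randomised, say so and give power after the assumed loss (about 81% at 10%).

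Restricting the 400 to screen failures before settling this would remove the reserve that 5c appears to intend.

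Under either choice, specify that all randomised patients are analysed in the assigned arm whatever operative or post-operative treatment changes occur, that they are not replaced, and how missing 30-day SSI status is handled.

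The cost is wording and possibly a slightly less favourable stated power. No patients are added beyond the 400 already foreseen.
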